**The Effect of Using Two Different Suturing
Techniques on Free Gingival Marginal Stability
after Esthetic Crown Lengthening for Treatment
of Gummy Smile
(Randomized Clinical Trial)**

Methodology

Document date: 3 /1/2020

Sample selection and assignment:

Thirty patients (26 females, 4 males), who were candidates for esthetic crown lengthening, participated in this prospective clinical trial.

The subject was recruited consecutively from the outpatient clinic of Oral Medicine, Periodontology, oral Diagnosis and Radiology Department, Faculty of Dentistry, Ain Shams University and faculty of dental medicine, Misr international University. The purpose of the study was explained to all patients and an informed consent was signed before the conduction of the study. The proposal was presented to the faculty of Dentistry Ain Shams University Research Ethics committee and was approved before starting the research ()

Patient selection:

Inclusion Criteria:

1. Patients complaining from gummy smile (altered passive eruption)
2. Age range (21-40) years.

3. Bone level is 2 mm or less from the cemento enamel junction
4. Teeth included were free from any periodontal destruction
5. Good compliance with the plaque control instructions following initial therapy.
6. Availability for follow up and maintenance program.

Exclusion criteria:

1. Presence of systemic diseases which could influence the outcome of the therapy (*American society of anesthesiologists I, ASA I*).
2. Patient suffering from periodontitis stage 4 grade C.
3. Presence of smoking habit.
4. Presence of occlusal interferences.
5. Pregnant females and lactating females. .
6. Vulnerable groups of patients (handicapped, mentally retarded and prisoners).
7. Restored teeth.

Grouping Criteria:

The study consisted of two groups the number of patient was determined by sample size calculation through G power analysis (15 patients). Patients were randomly selected using computer generated randomization (www.randomizer.org).

Group 1 (15 patients) (Periosteal suture) :

Esthetic crown lengthening procedure: internal bevel, sulcular and interdental incisions, flap elevation, bone removal then External vertical mattress suture was done (periosteal suture).

Group 2 (15 patients) (Figure of eight suture) :

Esthetic crown lengthening procedure: internal bevel, sulcular and interdental incisions, flap elevation, bone removal then modified interrupted suture was done (Figure of eight suture).

III- Assessments:

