1-Clinical parameters:

For the selected sites, the following clinical parameters were assessed preoperative (baseline) 3 and 6 months after surgical procedure.

1. Plaque index *Silness and Löe 1964*
2. Gingival Index *Löe and Silness 1963.*
3. Probing depth (PD) *Glavind and Loe, 1967*
4. Length of Attached gingiva

2-Esthetic outcome evaluation:

The following parameters were assessed 1, 3 and 6 months after surgical procedure:

- Level of the gingival margin (GM) through measurement of the crown length from the reference point in the surgical stent to the gingival margin (*Deas et al., 2004*).
- Marginal tissue contour (MTC) using root coverage esthetic score (RES) system (*Cairo et al. 2009*): Zero points = irregular gingival margin (does not follow the CEJ); 1 point =proper marginal contour/scalloped gingival margin (follows the CEJ).

- Papillary fill using classification of papillary fill (*Jemt 1997*) which it's score is as follows:
 - PIS1: entire papilla missing, lack of convexity
 - PIS 2: fills less than the interdental space, slight convexity.
 - PIS 3: fills more than half the interdental space but no complete fill
 - PIS 4: papilla fills the entire space, harmonic gingival contour
 - PIS 5: hyperplastic papilla covering too much tooth structure, irregular tissue contour
- Patient satisfaction prior surgery and 6 months post-surgery (*Silva et al., 2015*).

Patient satisfaction criteria

Prior to surgery

- How would the patient rate the gun shown when smiling, size of the upper teeth, the length of upper teeth and the width of it (way too little, too little, about enough and too much way too much)

After surgery

- Is the patient satisfied with the gingival display during talking and smiling, teeth display during

Material and Method

talking and smiling (not at all, slightly, somewhat, very and extremely).

- How was the procedure experience (much worse, worse, same as I thought, better and much better).

Presurgical therapy:

- Full Conventional periodontal treatment including supra, subgingival scaling and root planning were performed using hand scalers and curettes.
- Oral hygiene instructions(regular brushing 3 times/day, flossing and using mouthwash) were repeated until patients had achieved a proper level of oral hygiene where plaque index (PI) ≤ 1 .
- Teeth were examined for caries, periapical infection and restorative procedures in order to be treated.

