- Assessment parameters were recorded prior to surgery using UNC-15* manual probe (Hu Friedy)
- Alginate impressions were made 4 weeks following initial therapy of each maxillary arch to fabricate customized probing stents. Full-arch probing stents were made on stone casts Stents were trimmed to the height of contour, and

* PCPUNC15 Single-ended, color-coded probe. ergonomic handle. University of North Carolina, Hu Friedy, USA.

Material and Method

grooves were placed at sites to be measured with a narrow fissure bur to act as reference points for clinical parameters assessment.

(IV) Surgical procedures

Group (1)

- 1) Anesthesia (Articaine HCL 4% containing epinephrine at a concentration of 1:100,000)[†] was administrated at the selected teeth.
- 2) The tooth width to length ratio was determined according to the golden proportions (RED: The successive width proportion, when viewed from the facial aspect, should remain constant as we move posteriorly from the midline) (***Ward 2001***)
- 3) Bone sounding was done(patient was given anesthesia probing until the bone level was done using UNC-15[‡] manual probe) to determine the bone position in relevance to the CEJ position then bleeding points were done to determine the amount of the gingival tissue that was removed

[†] Artinibsa 4%cartouches de 1.8ml ,inibisa dental.

[‡] PCPUNC15 Single-ended, color-coded probe. ergonomic handle. University of North Carolina, Hu Friedy, USA.

Material and Method

- 4) Primary submarginal incision, secondary intrasulcular then tertiary incision at the papillary area were done using the surgical blade (15c)[§]
- 5) Full thickness flap reflection at the crestal bone area using mucoperiosteal ** elevator was done, while at the papillary area partial thickness flap using the surgical blade (15c)^{††} was done.
- 6) After flap reflection the supracrestal soft tissue were removed using surgical curette^{‡‡} (universal curette 2R/2L,4R/4L)
- 7) Ostectomy 3mm from the cemento enamel junction were performed using end cutting burs^{§§}. Root surfaces were scaled to remove remnants of supracrestal connective tissue fibers.
- 8) Flap was repositioned by external vertical mattress (periosteal suture) suturing technique using resorbable 5-0 vicryl sutures^{***}

[§] Trinon sterile scalpel Blades ,lot0483,Germany

^{**} Buser Periosteal handle #6, Hu- Friedy, USA.

^{††} Trinon sterile scalpel Blades ,lot0483,Germany

^{‡‡} Universal Curettes(2R/2L),(4R/4L), Hu-Friedy ,USA

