^{§§} Midwest operative Carbide burs,FG,End cutting, #957,1.0mm diameter,3.7mm length,10/Pkg,Dentsply Midwest,Patterson item#493-0079,Mfg item#:389278.

^{***} Assut Sutures, Absorbable (PGA) 5-0 USP, braided violet coated 3/8 rev.cutt.17mm, AM trading.

Fig (3): Showing diagram for the periosteal suture

Group (2)

- 1) Anesthesia (Articaine HCL 4% containing epinephrine at a concentration of 1:100,000)^{†††} was administrated at the selected teeth.
- 2) The tooth width to length ratio was determined according to the golden proportions (RED).
- 3) Bone sounding was done to determine the bone position to in relevance to the CEJ position then bleeding points were done to determine the amount of the gingival tissue that was removed
- 4) Primary submarginal incision, secondary intrasulcular then tertiary incision at the papillary area were done.
- 5) Full thickness flap reflection at the crestal bone area using mucoperiosteal^{‡‡‡} elevator was done, while at the papillary area partial thickness flap using the surgical blade (15c)^{§§§} was done.

^{†††} Artinibsa 4% cartouches de 1.8ml ,inibisa dental.

^{‡‡‡} Buser Periosteal handle #6, Hu- Friedy, USA.

^{§§§} Trimon sterile scalpel Blades ,lot0483,Germany

Material and Method

- 6) After flap reflection the supracrestal soft tissue were removed using surgical curette**** (universal curette 2R/2L,4R/4L)
- 7) Ostectomy 3mm from the cemento enamel junction were performed using end cutting burs††††. Root surfaces were scaled to remove remnants of supracrestal connective tissue fibers.
- 8) Flap was repositioned by modified interrupted (figure of 8 suture) suturing technique using resorbable 5-0 vicryl sutures††††.

[figure not shown]

Fig (4): Showing a diagram for the interrupted modified sutur

**** Universal Curettes(2R/2L),(4R/4L), Hu-Friedy ,USA

†††† Midwest operative Carbide burs,FG,End cutting, #957,1.0mm diameter,3.7mm length,10/Pkg,Dentsply Midwest,Patterson item#493-0079,Mfg item#:389278.

††† Assut Sutures, Absorbable (PGA) 5-0 USP, braided violet coated 3/8 rev.cutt.17mm, AM trading.

V-Postoperative care:

- All patients had received antibiotic for 1 week
(Augmentin 1 gm every 12 hours\$\$\$\$, metronidazole ***** 500gm every 12 hours) and analgesics(Brufen ††††† 400 every 8 hours) were prescribed for the patient and instructed to avoid brushing at the surgical site

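### The arms differ only at the suture (step 8), but the plan describes nothing that keeps the allocation from the surgeon during cutting, and no later reading shows both arms were cut alike

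*Combined protocol and SAP*

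**What the plan says.** **Allocation.** Under Grouping Criteria, randomisation is one sentence: "Patients were randomly selected using computer generated randomization", followed by a website. Nothing is said about concealment, when the assignment is opened, or who opens it.

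**Cutting.** In section (IV), Surgical procedures, both groups have the same steps 1 to 7; the Group 2 text only leaves out some instrument detail and explanation. At step 3 bone is sounded and "bleeding points were done to determine the amount of the gingival tissue that was removed". The incisions follow at step 4. Step 7 in both groups reads "Ostectomy 3mm from the cemento enamel junction were performed using end cutting burs". Inclusion criterion 3 is "Bone level is 2 mm or less from the cemento enamel junction".

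**Where the arms part.** Step 8 in Group 1: "Flap was repositioned by external vertical mattress (periosteal suture) suturing technique using resorbable 5-0 vicryl sutures". Step 8 in Group 2: "Flap was repositioned by modified interrupted (figure of 8 suture) suturing technique using resorbable 5-0 vicryl sutures".

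**Measurement.** The margin outcome in section III is "Level of the gingival margin (GM) through measurement of the crown length from the reference point in the surgical stent to the gingival margin", listed at 1, 3 and 6 months. Section VI has a separate operator score the outcomes after surgery. No step after the ostectomy reads the bone level, bone level is in neither assessment list, and no margin reading at closure is listed.

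**The concern.** The trial asks whether the suture affects the gingival margin. Two earlier decisions also set that margin: how much gingiva is removed (steps 3 and 4) and where the bone is cut (step 7). Randomisation balances the patients who arrive at surgery. It does not balance what a surgeon does after learning the arm, and a separate outcome scorer protects the reading, not the cutting.

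A surgeon who knows the arm could cut more, or less, where one suture is expected to hold the margin less well. The consequence runs in either direction. If the sutures are equivalent, uneven cutting can pass for a suture effect. If they do differ, compensating cutting can hide the difference. Because nothing is read after the cut or at closure, a month-1 difference mixes cutting, suture and healing, and the data the plan describes could not separate them.

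**Working it through.** **Is there room for uneven cutting?** The target is 3 mm from the CEJ and entry allows at most 2 mm, so the minimum bone removal is 3 − 2 = 1 mm. Included sites therefore all need operator-dependent cutting before the arms part.

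**Is there a reading that would show it?** Bone is read at entry and at step 3 ("Bone sounding was done to determine the bone position to in relevance to the CEJ position" in Group 2, with the same sounding in Group 1). Both readings precede the cut. Step 7 states a target, which is not a check that the target was met.

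**The plan's own figure.** The 15 per group cannot be reproduced, because no effect size, SD, power or sidedness is given. Solving backwards (two-sample t test, two-sided alpha 0.05 assumed, 28 df), 15 per arm gives 80% power at a standardised difference of 1.06.

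**Size of the effect (illustrative).** The documents give neither an SD nor a shift, so both are assumptions. Let d be the arm difference in margin level in SD units.

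- Critical value t(0.975, 28) = 2.048.
- Standard error in SD units = √(2/15) = 0.365.
- Noncentrality = d / 0.365.
- P(reject) = P(|T| > 2.048), with T noncentral t on 28 df.

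| Situation | d | Noncentrality | P(reject) |
|---|---|---|---|
| No suture effect, even cutting | 0 | 0 | 5.0% |
| No suture effect, cutting shift 0.25 SD | 0.25 | 0.685 | 10.1% |
| No suture effect, cutting shift 0.5 SD | 0.50 | 1.369 | 26.2% |
| Real effect 1.06 SD, even cutting | 1.06 | 2.903 | 80.0% |
| Real effect, opposing shift 0.25 SD | 1.06 − 0.25 = 0.81 | 2.218 | 57% |
| Real effect, opposing shift 0.5 SD | 1.06 − 0.5 = 0.56 | 1.534 | 32% |

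Section VII also uses the Mann-Whitney test. In 40,000 simulated trials with normal data, its false-positive rates were 9.3% at 0.25 SD and 24.2% at 0.5 SD, so the choice of test changes little.

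In millimetres, 0.25 SD is 0.25 × 0.5 = 0.125 mm at an assumed SD of 0.5 mm, and 0.25 mm at an assumed SD of 1.0 mm. Both are small beside the 1 mm or more of bone removed.

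**What a post-cut bone reading could show.** The 95% CI half-width for the arm difference in final CEJ-to-crest distance is 2.048 × SD × 0.365.

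| Assumed SD of final distance | Half-width | Power to detect a true 0.5 mm difference |
|---|---|---|
| 0.25 mm | 0.19 mm | over 99% |
| 0.5 mm | 0.37 mm | 75% |
| 0.75 mm | 0.56 mm | 42% |

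**The case against.** **Discretion is limited.** Both arms share the tooth-proportion rule (step 2), the bone sounding (step 3) and a fixed 3 mm from an anatomical landmark (step 7). This stands. It narrows the room for uneven cutting but does not close it, because a shared target does not show that the target was met equally.

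**The title concerns stability.** Section VII analyses differences and percent changes. This also stands in part: change from month 1 to month 6 is exposed only to the part of a cutting shift that appears after month 1. The rates above are for margin level and should not be carried over to that change.

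**The magnitude is generic.** The shift and SD are assumed, and the same figures would apply to any trial with 15 per arm. That is correct; they show sensitivity and are not an estimate for this trial.

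**Surgery may be over.** The text is in the past tense and reports who took part. If so, late disclosure cannot be adopted, and only reporting remains.

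Two stronger readings are tempting. A reader might infer that the surgeon knew the arm, or cut the groups differently. The documents are silent on when the arm was opened, and silence is not evidence of either. A reader might also infer that the unadjusted comparison is invalid because pre-surgical bone level is not a covariate. It is not invalid: randomisation covers chance differences in bone level. A reading taken before the cut also could not detect or remove uneven cutting.

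**Conclusion.** The concern holds as a missing safeguard in the trial's one comparison. On the text, the arms differ only at step 8, nothing described keeps the allocation from the surgeon before then, and no reading after the ostectomy or at closure shows that the cutting matched. It is not a finding of bias.

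If a shift in margin level of a quarter to half an SD did arise from cutting, the false-positive rate would be about 10% to 26% instead of 5%, or 80% power would fall to about 57% to 32%, depending on direction. These figures assume a two-sided t test, 15 per arm with complete data, and shifts that the documents neither give nor rule out. The change should be made because it is nearly free and removes this route to bias at its source. Confidence is medium, since the surgeon may in fact have been unaware of the arm.

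**What to change.** 1. **Disclose late.** Release the suture allocation to the surgeon only after step 7 is complete, for example from a sealed envelope opened by an assistant. Both arms use the same 5-0 suture, and no listed step or material needs the arm earlier.
2. **Record the cut.** With the flap open and the arm still undisclosed, probe and record the CEJ-to-crest distance with the UNC-15 probe already in use. Keep the step 3 sounding as data. Tabulate both by arm as a fidelity check on cutting.
3. **Record the margin at closure.** Read the stent-to-margin distance once the flap is sutured and report it by arm as the starting point for stability. It follows suturing, so it also reflects the suture and is not a pure check on cutting.
4. **Leave the rest alone.** Use none of these readings as a covariate. The 3 mm target, the sample size and the planned tests stay as they are.

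**Cost.** One envelope and a few minutes of probing per patient. The bone table can show only gross differences (about ±0.37 mm at an assumed SD of 0.5 mm), but late disclosure does not depend on it.

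**If surgery is complete.** State whether the surgeon knew the arm before step 8 and show any soundings that were kept, by arm. If the surgeon did know, or this cannot be established, say in the conclusion that a suture effect cannot be separated from a difference in cutting.

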- Patients were instructed to rinse twice daily with Tantum verde[■] mouth rinse or hot saline mouthwash and to avoid mechanical plaque removal at the site of surgery
- Sutures were removed after 2 week.
- Patients were instructed not to brush for 2 weeks and not to floss the surgical area for 4 weeks.
- After 15 days patient were instructed to use modified bass technique for tooth brushing (***Carranzaa 12th edition***)

\$\$\$\$ Augmentin 1gm,Medical union pharmaceuticals(MUP) Egypt under license from ,Glaxosmithkline

***** Flagyl 500 mg, sanafi Aventis Egypt under license of sanafi Aventis French.

††††† Brufen 400mg, Al kahira pharm. and chem.Ind.Co. under license from abbott laboratories

[■]Tantum Verde Mouthwash and Gargle(Benzydamine hydrochloride 0.15g): Bottle of 125 ml, Eipico Egypt under license of A.C.R Angelini Francesco.SpA.Italy

VI-Postoperative evaluation and assessment:

Monthly recall appointments were scheduled

- The follow up period included oral examination, plaque and calculus removal when necessary
- Clinical and esthetic parameters were evaluated and scored by a separate operator at 1, 3 and 6 months postoperative the patient satisfaction was evaluated 6 months post-operative only
- All data were statistically analyzed

VII-Statistical analysis:

Statistical analysis was then performed using a commercially available software program (SPSS 18; SPSS, Chicago, IL, USA).

Values were presented as mean, standard deviation (SD), median, range and confidence intervals. Data were explored for normality using Kolmogorov-Smirnov test of normality. For parametric data, Independent t test was used for 2 group's comparisons, while ANOVA test was used to compare different observations.

Material and Method

Plaque and gingival indices and most values of difference and percent change were non-parametric and were compared using Mann Whitney U test for intergroup comparisons, while Friedman test and Wilcoxon signed Rank test were used for intragroup comparisons

Qualitative data were expressed as frequencies and percentages and were compared using Chi square test

The level of significance was set at $P \leq 0.05$.

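### Does the gm/mg mismatch between the metronidazole entry and its product footnote call for a change to the plan?

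*Combined protocol and SAP*

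**What the plan says.** Section V (Postoperative care) describes one drug regimen for the whole trial, with no split by suture group: "All patients had received antibiotic for 1 week". Three drugs follow in a single sentence, each with a marker to a product footnote.

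- Augmentin: the text has "Augmentin 1 gm every 12 hours" and the footnote "Augmentin 1gm,Medical union pharmaceuticals(MUP) Egypt".
- Metronidazole: the text has "500gm every 12 hours" and the footnote "Flagyl 500 mg, sanafi Aventis Egypt".
- Brufen: the text has "400 every 8 hours", with no unit, and the footnote "Brufen 400mg, Al kahira pharm".

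The section is written in the past tense, as is the rest of the methodology. The amount of metronidazole appears nowhere else.

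**The concern.** The same number carries two different units, and the document's own marker joins the two entries, so no knowledge of the brand is needed to see the clash. Nor can gm be excused here as a loose way of writing mg. The Augmentin entry uses gm for gram in both text and footnote, while the metronidazole and Brufen footnotes use mg. The document therefore treats them as separate units.

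This is also the only statement of the amount of a systemic drug reported for every participant. A reader who wants the amount per administration must choose between the text and the footnote. If the regimen were copied from this record, a unit conflict could travel with it. A thousandfold difference in a drug line would normally get any reviewer's attention.

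**Working it through.** No sample-size, power or error-rate figure is involved, so there is no derived figure of the plan to reproduce. The check is a comparison of units, followed by a check of where the amount could enter the trial's results.

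**Step 1: text against footnote.** All inputs come from section V and its product footnotes, with gm read as gram.

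| Drug | Text | Footnote | Text ÷ footnote |
|---|---|---|---|
| Augmentin | 1 gm | 1 gm | 1,000 mg ÷ 1,000 mg = 1 |
| Metronidazole | 500 gm | 500 mg | 500,000 mg ÷ 500 mg = 1000 |
| Brufen | 400, no unit | 400 mg | not computable; the numbers agree |

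One entry of three conflicts. The Brufen text only leaves out a unit that its footnote supplies, so it is an omission and not a contradiction.

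**Step 2: what the ratio means.** The text gives an amount per administration and the footnote gives the strength of a product. These need not be equal, since more than one unit of a product can be taken at a time. The 1000 therefore measures the unit mismatch. It does not measure an error in what anyone received. The firm finding is narrower: same number, different unit symbol.

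**Step 3: could the amount reach the results?**

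- *Outcomes.* The Assessments section lists plaque and gingival indices, probing depth, attached gingiva, gingival margin level measured from the stent, marginal contour, papillary fill and patient satisfaction. None is calculated from a drug amount.
- *Sample size.* The section on grouping gives 15 patients per group from a power calculation. Drug amount is not mentioned as an input.
- *Analysis.* Section VII plans t tests, ANOVA, Mann-Whitney, Friedman, Wilcoxon and chi-square tests. None uses the drug regimen as a covariate or a factor.
- *Comparison.* The regimen is stated once for both groups. If background care shifts an outcome by an amount *c* in each group, the contrast is (μ₁ + *c*) − (μ₂ + *c*) = μ₁ − μ₂, so *c* drops out. If the shift differed between groups, the contrast would still be the randomised effect of suture technique under the care actually given. Correcting the written unit would not alter that care.

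**Step 4: would a correction change conduct?** The section reports treatment already given. A corrected unit would alter the description and not the treatment.

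**The case for a change.** The strongest case for acting is that the defect is certain, costs one line to correct, and concerns a drug reported for all 30 participants. The text is running prose with number and unit intact, and the five-asterisk marker matches in both places, so it cannot be put down to a broken table or a redaction. Nothing else in the document resolves it. On that view even a probable typing slip should be corrected, because dose units in a public record ought not to be ambiguous.

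Most of this stands. The inconsistency is genuine, and the two places must be reconciled by those who hold the treatment records. What does not stand is the step from there to a deficiency in the plan.

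- The hazard to someone copying the regimen is conjectural. The document reports past care and does not direct future dosing, and the product footnote belongs to the same section. The literal text, 2 × 500 g = 1,000 g a day, is large enough to send a reader to that footnote.
- Adding Brufen to say that two of three entries need correcting merges a missing unit with a conflict.
- Nothing in the document shows that any patient received an unintended amount.

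**Conclusion.** The mismatch is real but clerical: one unit symbol in one of three drug entries, a literal ratio of 1000 between an amount given and a product strength. Its effect on the design, the sample size, the between-group comparison and the planned tests is nil. The metronidazole text and its footnote should be made to agree whenever the document is next edited. That is an editorial matter, and no amount is endorsed or proposed here.

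This rests on three readings of the document: that gm means gram, as the Augmentin entry indicates; that one regimen was given in both suture groups, as section V states; and that the section records completed care. If the treatment records showed that the groups had been given different regimens, that would be a different and more serious question, but nothing in the document suggests it.

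### Four outcomes have a preoperative baseline, but groups are compared only by unadjusted tests on values, differences and percent changes; a baseline-adjusted 6-month comparison should be the main one, with percent change descriptive.

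*Combined protocol and SAP*

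**What the plan says.** Section III (Assessments, Clinical parameters) covers plaque index, gingival index, probing depth and length of attached gingiva: "For the selected sites, the following clinical parameters were assessed preoperative (baseline) 3 and 6 months after surgical procedure". It does not say how several sites in one patient are combined.

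Section VII (Statistical analysis) names two between-group tests for numeric outcomes. The first is "For parametric data, Independent t test was used". The second is the Mann-Whitney test, used for the two indices and also because "most values of difference and percent change were non-parametric and were compared using Mann Whitney U test for intergroup comparisons". ANOVA is named for comparing observations, Friedman and Wilcoxon for changes within a group, and chi-square for qualitative data. No ANCOVA, regression, mixed model or covariate appears, and no form of an outcome is named as deciding.

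Two other places bear on how much the baseline can tell. Under Presurgical therapy, hygiene instruction continued until the plaque index was 1 or less. Section VI adds: "The follow up period included oral examination, plaque and calculus removal when necessary".

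**The concern.** The trial has 15 patients per arm and a baseline for four outcomes, yet the plan never uses that baseline as a covariate. It uses it only by subtraction or division. Which unadjusted form is more precise depends on the correlation between baseline and follow-up. The documents do not give it, so choosing the final value or the change is a guess, and a wrong guess is expensive at this sample size.

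Three forms of the same outcome may also give three different answers, and the plan does not say which one counts. Percent change has a further weakness: it cannot be computed when the baseline is 0, and no handling is stated. The plan does not say for which variables percent change was calculated. If plaque index is one of them, the presurgical limit allows a baseline of 0.

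**Working it through.** **The plan's own figure.** The plan gives 15 patients from a G power calculation, with two groups of 15. No effect size, SD, power or sidedness is stated, so the number cannot be reproduced. Solved backwards with the noncentral t distribution (two-sided 0.05), 15 per arm detects 1.06 SD at 80% power and 1.23 SD at 90%. This neither confirms nor refutes it.

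**Inputs.** From the documents: n = 15 per arm and significance level 0.05. Assumed: two-sided testing, normal data, equal SDs, a true difference d = 0.8 SD at 6 months, and a baseline to 6-month correlation r from 0 to 0.8.

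**Formulas.** Noncentrality, with √(15/2) = 2.739:

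- final value: d × 2.739, df 28
- change: d × 2.739 / √(2(1 − r)), df 28
- ANCOVA: d × 2.739 / √((1 − r²)(1 + 1/26)), df 27. The factor 1 + 1/26 is the average cost of estimating the slope with 30 patients.

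At d = 0.8 and r = 0.5 these are 2.19 for the final value, 2.19/√1 = 2.19 for the change, and 2.19/√(0.75 × 1.0385) = 2.48 for ANCOVA.

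**Power at d = 0.8**

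| r | Final value | Change | ANCOVA | ANCOVA minus better form |
|---|---|---|---|---|
| 0 | 56% | 32% | 54% | −2 points |
| 0.2 | 56% | 39% | 56% | 0 |
| 0.3 | 56% | 43% | 58% | +2 |
| 0.5 | 56% | 56% | 67% | +11 |
| 0.7 | 56% | 78% | 83% | +5 |
| 0.8 | 56% | 92% | 93% | +2 |

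Taking the wrong unadjusted form costs 56 − 32 = 24 points at r = 0 and about 35 points at r = 0.8 (91.7 − 56.2). At d = 0.5 the same formulas put ANCOVA between 1 point below and 6 points above the better form.

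**Width of the 95% interval.** The half-width for the final value is 2.048 × √(2/15) = 0.75 SD. For ANCOVA it is 0.66 SD at r = 0.5 and 0.76 SD at r = 0.

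**Why the forms can disagree.** With 15 per arm the chance baseline difference has a standard deviation of √(2/15) = 0.37 SD, and exceeds 0.5 SD in about 17% of trials. Given a 0.5 SD imbalance and r = 0.5, the final-value comparison is shifted by 0.5 × 0.5 = +0.25 SD and the change comparison by (0.5 − 1) × 0.5 = −0.25 SD. The adjusted comparison is not shifted. These shifts average to zero over randomisations.

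**Rank methods.** A simulation with 4,000 trials per setting used an assumed mean of 2 and SD of 0.5, normal data and a 0.8 SD difference. Power at r = 0.3 / 0.5 / 0.7 was:

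- Mann-Whitney on the final value: 53/53/53%
- Mann-Whitney on the change: 39/53/75%
- Mann-Whitney on percent change: 35/47/68%
- rank ANCOVA: 56/64/78%

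With no true difference, rank ANCOVA rejected in 5.0 to 5.8% of trials. The ordering agrees with the table. The assumed distribution is not that of any outcome in this trial, so these figures only illustrate the direction.

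**The case against.** The strongest reply is that unadjusted tests are valid in a randomised trial and that the plan already uses the baseline by testing differences. The first half stands in full. The second stands in part: a difference is an adjustment with the slope fixed at 1, which is efficient only when the correlation is high.

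A second reply is that the gain is uncertain and may be small. This also stands. Plaque index was held to 1 or less before surgery and plaque is removed at recalls, so its correlation with follow-up may be low. Gingival index is taken after initial therapy, and probing depth in teeth without periodontal destruction, so both baselines may be narrow too. These are supporting outcomes; the title outcome is the gingival margin.

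A reader might infer more than the documents support:

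- *That the results are biased or the error rate inflated.* Randomisation rules this out for any single unadjusted comparison. Testing three forms would raise the error rate only if any one of them could count as success, and the plan does not say so.
- *That sites were analysed as independent.* The plan does not state the unit of analysis. One value per patient is a specification that the adjusted model needs, not a correction of a stated error.
- *That the same remedy carries over to the gingival margin, with the 1-month reading as reference.* The esthetic list says "The following parameters were assessed 1, 3 and 6 months after surgical procedure", while Presurgical therapy says "Assessment parameters were recorded prior to surgery using UNC-15" without naming the parameters. Whether a preoperative margin reading exists is unclear. The 1-month reading follows the suture and may already carry its effect, so randomisation does not make it comparable between arms.
- *That percent change of plaque was computed from zero baselines.* The documents do not say which variables were used or whether a zero occurred.

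**Conclusion.** The point holds as a recommendation on precision and clarity for four outcomes. The text contains no baseline-adjusted group comparison and no deciding form. At 15 per arm and an assumed 0.8 SD, adjustment ranges from a loss of about 2 points of power to a gain of about 11 against the better unadjusted form. Its main value is protection against the wrong form, which costs 24 points at r = 0 or about 35 at r = 0.8. Every correlation and the effect size are assumptions. The benefit is least certain for plaque index and may be small for gingival index and probing depth. Nothing here shows that the planned tests are invalid.

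**What to change.** For plaque index, gingival index, probing depth and attached gingiva:

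1. Use one value per patient, for example the mean over the selected sites.
2. Name the baseline-adjusted 6-month comparison as the main one. Sections III and VI differ on whether clinical parameters were also taken at 1 month, but both include 6 months.
3. For probing depth and attached gingiva, fit ANCOVA of the 6-month value on group and baseline, and report the adjusted difference with its 95% confidence interval.
4. For plaque and gingival indices, use rank ANCOVA or ordinal regression with baseline.
5. Report percent change descriptively, without a between-group test.
6. Section VII is written in the past tense and describes how the data behaved. If data had been examined, label the adjusted analysis post hoc; it then carries less weight than a prespecified one.

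The cost is one degree of freedom per model, up to about 2 points of power if the correlation is below about 0.2, and the loss of tooth-level detail. No new data are needed, and the SPSS software named in the plan can fit ANCOVA.
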